#### (intervention) or invitation for fast-track HIV testing (standard of care, SOC)

Pregnant women will be randomized to give their male partners either an invitation letters for a wellness visit (Arms 3 and 4) or an invitation letter for fast-track HIV testing to give to their male partners ((Arms 1 and 2). The objective of this intervention is to evaluate the implementation and outcomes of invitation letters offering dual syphilis and HIV testing, blood pressure and visual acuity as part of a wellness visit, compared letters for fast-track HIV testing in the antenatal clinic (SOC).

#### Invitation of male partners to wellness visit (intervention group)

Pregnant women in the intervention group will be provided an invitation letter to give to their partner detailing information on services provided during a wellness visits at the ANC. Services will include dual syphilis and HIV testing and treatment, hypertension screening, a vision exam, and COVID-19 symptom screening. The wellness letter will include infographics to depict these services in an engaging way and appeal to men who have low levels of literacy or are illiterate. These invitation letters will be pre-tested on men, including those enrolled in the Obumu study, to elicit feedback on content and layout.

#### Invitation of male partners for fast-track HIV testing (standard of care group)

Women in the control arm will be provided letters to deliver to their partner to invite them to come for HIV testing to the ANC clinic for fast-track testing at Kitebi, alone or as a couple (standard of care). Fast track testing will allow men to show up to the clinic with their invitation card and receive HIV testing and counseling without having to go through the normal clinic flow, thus minimizing time at the facility. Similar to the intervention group, invitation letters will include positively framed messages to men about the opportunity to receive PrEP and ART if they get tested. Letters will also include information on how to contact a 24-hour “helpline” to talk with a counselor about the meaning of results and referrals. Invitation letters will have unique numbers to allow linkage of the man’s testing to his partner.

#### HIVST kits

[figure not shown]
Following current MOH guidelines for secondary distribution of HIVST in ANC clinics, all women will be given one or two HIVST kits to bring home to their partner. They will be provided a brief demonstration of how to use the self-test and will be given two oral fluid based HIV self-tests (Oraquick rapid HIV-1/2 test kit with developer fluid vial and stand) to take home with written and pictorial instructions translated into Luganda (the local language) about HIVST to share with their partner. The instructions will indicate how to perform an oral swab, how long to wait to read results, and how to interpret the results. Women will receive information about HIV self-testing including reasons for suggesting usage of the self-test to their partner, and strategies for introducing self-tests to their partners; however, it will also be emphasized that women are not obligated to encourage their partner to use the self-test. Because use of self-tests at home will mean that a trained counselor will not be present when women or their partners take the test, the counselor will discuss messaging with women, so that she and her partner can use the self-tests correctly and safely on their own. A counselor will be available by phone if a woman in the self-test arm needs help explaining counselling messages to their partner. The messages and counseling that we will provide will adhere to Uganda National Guidelines for HIV Testing Services.

#### Antenatal and postnatal care

Data collection will occur during standard of care antenatal/postnatal visits. HIV-positive pregnant women will access routine care at antenatal clinics according to guidelines for preventing and treating HIV infection in Uganda (64). Pregnant women will have up to 4 antenatal visits before delivery with 1 visit in the first trimester, 1 visit in the second trimester and 2 visits in the third trimester. The standard- of-care antenatal package includes cotrimoxazole preventive therapy, nutrition assessment, iron, folic acid and multivitamin supplementation and screening for syphilis. Women newly initiating ART in PMTCT B+ will have same-day pre-ART adherence counselling and ART initiation (Table 1). They will have PMTCT B+ follow-up

visit two weeks after initiating ART, and monthly visits for ART refills thereafter until delivery. Women will be offered delivery at a facility of their choice. Women randomized to the POC VL arm will receive POC VL testing at her delivery, as well as POC EID testing for her infant. After delivery, women will be followed quarterly for up to 6 months. Women in both arms will be screened for COVID-19 symptoms, and those with symptoms will be tested by SARS-CoV-2 PCR and those without symptoms will be screened for antibodies. Those who are PCR positive will be referred to a medical officer for clinical evaluation and contact tracing.

Brief study questionnaires will be administered will occur at the PMTCT visits to avoid separate study-specific visits. Postnatal care and infant immunization visits will follow the routine maternal and child health (MCH) schedule. Viral load (VL) monitoring will include POC VL testing at enrollment, delivery, and every 6 months until M6 post-partum for women randomized to the intervention arm, and laboratory HIV RNA testing at enrollment, and every 6 months until M6 post-partum for women randomized to the control arm. Blood samples will be batch-tested at collaborating laboratories. Women will be asked about interruptions in ART use. If the mother is stable on ART with good adherence and undetectable VL, post-partum visits will be scheduled for week 6, and months 3 and 6. During these clinic visits, women will complete interviewer-administered surveys to collect data on behavioral factors that could mediate women's post-partum ART use. Women in the intervention arm will be provided their viral load results at that visit, and in the control arm will receive their viral load results at their next visit, in addition to counseling about the relationship between adherence, viral load and transmission risk.

## Management of Viral Load Results

Participants in the intervention arm will have all routine ART monitoring tests performed according to the schedule described in the SoC arm follow-up procedures, however the POC VL assays will be utilized instead of lab based VL testing. POC VL testing will be performed using Cepheid's GeneXpert® HIV-1 VL assay performed at the beginning of the clinical encounter, so the clinical examination can be performed during the 90 minutes required to run a GeneXpert HIV VL test. If the participant is not able to wait for the results, then the study team will allow the participant to leave the study clinic but will ask them to remain in the vicinity and return to the clinic for their VL results. Prior to consent and enrollment, all potential participants will be counseled on the study procedures to ensure participants are able to comply with Intervention Arm study procedures, including potentially spending more time in clinic to receive VL results than they normally would as part of SoC clinic procedures. The GeneXpert testing will be conducted in the adjacent clinic site laboratory. Results will be managed according to SoC South African guidelines.

The clinical decisions from the SOC VL testing will adhere to the Ugandan guidelines. The algorithm for the current VL monitoring guidelines is summarized below:

- HIV VL <50 copies/mL: Reinforce the importance of good ART adherence and continue routine VL monitoring
- HIV VL 50-999 copies/mL: Provide standard of care ART adherence counseling, provide ART,

and ask participant to return to the clinic in six months for repeat VL testing. If the VL remains high (50-999 copies/mL) upon repeat testing, then the participant should continue receiving enhanced adherence counseling and repeat VL testing every six months until viral suppression (<50 copies/mL) is achieved.

- HIV VL  $\geq 1,000$  copies/mL: Provide standard of care ART adherence counseling; provide ART and ask participant to return to the clinic in three months for repeat VL testing. If the VL remains high ( $\geq 1,000$  copies/mL) after repeat testing, then participants will be considered for switching to second line treatment according to Uganda guidelines.

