Our co-investigator, [name], demonstrated in the STREAM study among 390 PLWHIV in KwaZulu-Natal South Africa, that POC VL using the Cepheid Xpert HIV-1 viral load assay with same day adherence counseling by nurses (i.e., task shifting) was associated with a 13.9% increase in viral suppression and retention in care compared to the control group, which received VL results and counseling at their next visit.(26) There were no adverse events, both patients and providers preferred POC testing over lab-based testing, and POC VL testing was cost-effective compared to laboratory-based VL testing, which requiring 2-3 weeks turnaround.(27) POC VL testing enables real-time targeted ART adherence counseling but has not been evaluated among pregnant and postpartum women, for whom viral suppression is important not only for their own health, but also to reduce the likelihood of vertical HIV transmission.

In the Kingasa study, women randomized to have POC VL at enrollment, delivery and 6 months postpartum, will have a finger prick to obtain whole blood for the Cepheid Xpert HIV-1 RNA cartridge on the Xpert IV machine with results in 90 minutes. Women who are randomized to POC VL who have VL >200 c/ml will receive additional adherence counseling, following the STREAM protocol, [26] to address the challenges that they are having with ART use. At the delivery visit, infants of women in the POC VL arm will also have viral load testing done.

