## *Objectives*

**Aim 1: To determine the proportion of male partners of pregnant HIV-positive women who test for HIV at the clinic, based on invitation to a wellness visit (dual syphilis and HIV rapid test, blood pressure, visual acuity screening and COVID symptom screening, and if available, PCR testing for those with symptoms) compared to the standard of care (standard of care invitation letter for HIV fast track testing at the clinic).**

Innovations are needed to address the challenges associated with male partner engagement during their partner's antenatal and postpartum care periods. Provision of wellness visits providing STI testing and general health services, may overcome male partners reluctance to be tested in PMTCT clinics. We will randomize women 1:1 to the intervention and control arm and determine the proportion of male partners who test for HIV based on male enrollment numbers and data on HIV testing.

Primary outcome: The proportion of male partners who test for HIV compared by arms (comparing Arms 1 and 2 combined to Arms 3 and 4 combined).

**Aim 2: To evaluate whether POC viral load testing with same day ART adherence counseling improves ART continuation, and viral suppression among pregnant women living with HIV.**

Point-of-care viral load (POC VL) testing has been demonstrated to enable task-shifting and real-time adherence counseling. It is innovative to utilize POC VL for pregnant and post-partum women for real-time assessment of ART adherence, to improve ART use, retention in care, and viral suppression post-partum.

We will assess POC viral load monitoring and targeted ART adherence counseling compared to the standard of care laboratory-based HIV RNA testing, (comparing arms 1 and 3 combined to Arms 2 and 4 combined). Primary outcomes are viral suppression and HIV status disclosure at 6 months post-partum. *Hypotheses: POC viral load testing and same day adherence counseling will increase ART continuation and viral suppression*

Primary outcome: The proportion of HIV-positive women who are virally suppressed at 6 months post-partum. Viral suppression will be defined as plasma viral load <50 copies/ml.

**Aim 3: To evaluate whether engagement in care is improved among male partners who are provided a phone call follow up from a male counselor after HIV testing compared to standard of care.**

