**Table 5. Procedures for HIV-positive pregnant women**

	ANTENATAL				Delivery	POSTNATAL	
	T1	T2	T3	T4		M3	M6
ADMINISTRATIVE AND REGULATORY PROCEDURES							
Obtain written informed consent	[X]	[X]	[X]	[X]			
Assign participant identification number	[X]	[X]	[X]	[X]			
Assess eligibility	[X]	[X]	[X]	[X]			
Collect/update locator information	[X]	[X]	[X]	[X]		X	X
Collect/update demographic information	[X]	[X]	[X]	[X]			
Obtain random allocation	[X]	[X]	[X]	[X]			
Schedule next visit	[X]	[X]	[X]	[X]		X	X
COUNSELING							
HIV/STI risk reduction counseling, condom provision	[X]	[X]	[X]	[X]		X	X
Standard of care counseling (ART adherence, clinical & prevention benefits)	[X]	[X]	[X]	[X]		X	X
CLINICAL PROCEDURES							
Provide HIV test results	[X]	[X]	[X]	[X]			
Medical history	[X]	[X]	[X]	[X]		X	X
Perform physical exam	[X]	[X]	[X]	[X]		[X]	[X]
STI syndromic assessment and management	[X]	[X]	[X]	[X]		[X]	[X]
Referral for / provision of ART according to national guidelines	[X]	[X]	[X]	[X]		X	X
PMTCT PROCEDURES*							
Antenatal care package	[X]	[X]	[X]	[X]			
Postnatal care package						[X]	[X]
Infant HIV status at 6 weeks						X	
LABORATORY PROCEDURES							
Syphilis testing	X	[X]	[X]	[X]			
HIV serology	X	[X]	[X]	[X]			
Plasma HIV viral load (control arm)	[X]	[X]	[X]	[X]			X*
POC viral load (intervention arm) with same day ART adherence counseling	[X]	[X]	[X]	[X]	X		X

\*Standard of care

Study staff will perform study specific procedures at collaborating clinics

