**LEGEND**

[ ] as indicated

T = trimester

\* Point of care (POC) viral load with same day adherence counseling in the intervention arm and laboratory-based HIV VL and adherence counseling at the next visit in the control arm

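### As scheduled, the viral load behind the Aim 2 primary endpoint is a point-of-care test in the POC groups and a laboratory test in the controls, and no common endpoint assay or specimen is stated

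*Protocol*

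**What the plan says.** **Endpoint.** Objectives, Aim 2: "Viral suppression will be defined as plasma viral load <50 copies/ml". Outcome measurements adds that suppression is assessed at the 6-month postpartum visit. Neither place names an assay, platform or laboratory.

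**Test in the POC groups.** Management of Viral Load Results says that women in the intervention groups have the routine monitoring tests, "however the POC VL assays will be utilized instead of lab based VL testing". The assay is GeneXpert, and "The GeneXpert testing will be conducted in the adjacent clinic site laboratory". Table 5 has a row "POC viral load (intervention arm) with same day ART adherence counseling", marked at delivery and at month 6 (M6).

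**Test in the control groups.** Antenatal and postnatal care gives "laboratory HIV RNA testing at enrollment, and every 6 months until M6 post-partum for women randomized to the control arm". Table 5 has a separate row that begins "Plasma HIV viral load (control arm", marked at M6 and footnoted as standard of care. The Table 5 legend repeats the split: "laboratory-based HIV VL and adherence counseling at the next visit in the control arm". No platform is named for the controls.

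**Specimen.** The background section POC HIV Viral Load says that POC women "will have a finger prick to obtain whole blood for the Cepheid Xpert HIV-1 RNA cartridge on the Xpert IV machine". HIV seroconversion and Table 7, which concern male partners who seroconvert, describe the POC test as a plasma test.

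**Text that might imply a common test.** Antenatal and postnatal care mentions batch testing of blood samples at collaborating laboratories, with no arm stated. Table 2 lists HIV RNA testing of women at 6 months postpartum, and the text beneath it mentions 6-monthly HIV RNA monitoring, again with no arm stated.

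**The concern.** Aim 2 compares the proportion suppressed between women with and without POC testing. If the M6 value is read by one test in one group and by another test in the other, the observed difference is the effect of POC testing plus any difference between the tests at the 50 copies/ml cut-off. The test is determined entirely by the randomised factor, so no analysis of the scheduled data can separate the two. Randomisation does not balance the difference and a larger sample does not shrink it.

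The intervention does not need this arrangement. It works through results and counselling given earlier, and the M6 result cannot change the viral load in the sample it was read from. The POC result can guide same-day care at M6 while the endpoint is read another way.

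**Working it through.** **1. Does any scheduled test cover both groups at M6?**

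| Place in the protocol | POC groups at M6 | Control groups at M6 |
|---|---|---|
| Antenatal and postnatal care | POC | Laboratory HIV RNA |
| Management of Viral Load Results | GeneXpert, replacing the laboratory test | Laboratory |
| Table 5 and legend | POC row only | Plasma row only |
| Batch-testing sentence | Arm not stated | Arm not stated |
| Table 2 and text beneath | Arm not stated | Arm not stated |

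The three places that name an arm all split the test by arm. The two that do not name an arm do not mention the endpoint.

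**2. The plan's own power figures.** Inputs from the power section for viral suppression and Table 4: 200 women, so 100 v 100 for this factor; two-sided alpha 0.05; standard-of-care suppression 60/70/80%. With a pooled-variance two-proportion test, no continuity correction and no dropout, the differences giving 80% power are 18.2, 16.3 and 13.4 points. The protocol's 18, 16 and 13 reproduce. Power at exactly 60% v 78% is 79.0%.

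**3. Model for a difference between tests.** Let p be true suppression in the POC groups, q the share of suppressed POC women reading ≥50, and r the share of unsuppressed POC women reading <50. Both rates are net of the laboratory test and both are assumptions, because the documents give no agreement data.

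Observed POC suppression = p(1 − q) + (1 − p)r

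Bias = −pq + (1 − p)r

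With observed proportions p1 (control) and p2 (POC), SE0 = √(2·p̄(1 − p̄)/100), where p̄ is their mean, and SE1 = √([p1(1 − p1) + p2(1 − p2)]/100). The chance of a significant result favouring POC is 1 − Φ((1.96·SE0 − (p2 − p1))/SE1).

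**4. Suppressed women misread (r = 0).** Example with q = 5% and 60% v 78%: observed POC = 0.78 × 0.95 = 0.741, difference 0.141, SE0 = 0.0665, SE1 = 0.0657, power = 56.5%. With q = 2%: 0.78 × 0.98 = 0.7644, power 70.7%. If the same 5% error applied in every arm, power would be 72.4%.

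**5. Unsuppressed women misread (q = 0).** Example with r = 10%, no true effect, p = 60%: observed POC = 0.60 + 0.40 × 0.10 = 0.64, bias +4.0 points, SE0 = 0.0686, SE1 = 0.0686, false benefit 8.4%.

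**6. Range with no true effect, p = 60/70/80%.** Without misreading, false benefit is 2.5%.

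| q | r | Bias (points) | Significant for POC (%) |
|---|---|---|---|
| 2% | 0 | −1.2 / −1.4 / −1.6 | below 2.5 |
| 5% | 0 | −3.0 / −3.5 / −4.0 | 0.8 / 0.6 / 0.4 |
| 0 | 2% | +0.8 / +0.6 / +0.4 | 3.3 / 3.1 / 2.9 |
| 0 | 5% | +2.0 / +1.5 / +1.0 | 4.7 / 4.2 / 3.7 |
| 0 | 10% | +4.0 / +3.0 / +2.0 | 8.4 / 6.8 / 5.5 |
| 2% | 5% | +0.8 / +0.1 / −0.6 | 3.3 / 2.6 / 1.9 |
| 5% | 10% | +1.0 / −0.5 / −2.0 | 3.5 / 2.1 / 1.1 |

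Misreading suppressed women mainly loses power. Misreading unsuppressed women creates false benefit. Together they partly cancel.

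**The case against.** The strongest reply is that the substitution sentence concerns routine monitoring and care. The endpoint texts name no assay, and nowhere does the protocol say that the POC reading is the endpoint reading. The batch-testing sentence cannot describe a 90-minute on-site test, and the HIV RNA text at Table 2 has no arm restriction. A laboratory sample from every woman may have been intended, and an analysis plan or laboratory manual could say so.

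Much of this stands. A reader might infer that the protocol fixes a different endpoint test in each group, but the text does not go that far. What remains is that the batch-testing sentence directly follows the control-arm laboratory clause, that Table 2 concerns serodiscordant couples, and that neither mentions the endpoint. Table 5, the schedule that sites follow, lists no plasma viral load for the POC groups. An analysis plan can choose among the results that exist, but it cannot supply a sample that was not collected.

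A reader might also infer that the endpoint compares whole blood with plasma. Whole blood appears only in the background, and the seroconverter sections call the POC test a plasma test, so the specimen is unclear and a mismatch is not established.

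Finally, a reader might infer that the arrangement favours POC testing. With no agreement data and no named control platform, even the existence of a difference at 50 copies/ml is unknown.

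**Conclusion.** The point holds as a gap between the endpoint definition and the schedule. Followed as written, the schedule ties the test pathway to the randomised POC factor, and no common assay or specimen is stated for the primary endpoint.

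The size is illustrative only. With 100 evaluable women per group and standard-of-care suppression of 60–80%, the assumed rates give biases between −4.0 and +4.0 points, against planned effects of 13–18 points. At the low end (2% misread either way) the bias is between −1.6 and +0.8 points and power for 60% v 78% is still 71%. At the high end, power falls to 57% or false benefit rises to 8.4%. These figures rest on assumed error rates, and the documents support no particular rate or direction. The matter should be fixed because it affects a primary endpoint and because the sample has to be planned before the M6 visits.

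**What to change.** State one assay and one specimen type for the M6 endpoint in all four arms, and define <50 copies/ml on that reading. Keep the POC result for same-day care. There are two ways to do this:

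- **Common laboratory reading.** Include M6 plasma from the POC groups in the batch laboratory testing already mentioned. This keeps the plasma definition and costs about 100 extra laboratory viral loads and a plasma sample from each POC woman at M6.
- **Common Xpert reading.** Read the controls' M6 sample on the same platform and specimen as the POC groups. This adds no tests, but it replaces the controls' M6 laboratory test and leaves any Xpert misreading in both groups (power 72% in the 5% example). The Aim 2 definition must be amended if the specimen is whole blood, and the protocol must say how the controls' M6 result is handled.

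In either case, correct Table 5 and reconcile these places on endpoint assay and specimen: POC HIV Viral Load (background), Objectives, Antenatal and postnatal care, Management of Viral Load Results, Table 2 with the text beneath it, HIV seroconversion, and Table 7. If a common laboratory reading was always intended, one sentence and the Table 5 correction settle the main point, leaving only these wording changes.

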### *Recruitment*

IDI Kasangati has long-established recruitment and retention strategies to identify and enroll participants for prospective follow up. Recruitment materials will be approved by the IRB before study initiation. Recruitment materials will educate women about the benefits of male partner testing, the probability of being HIV serodiscordant, safety and efficacy of PrEP, and risks of post-partum ART discontinuation for the woman's health and the possibility of HIV transmission to her baby and partner.

Women attending antenatal care are offered HIV testing, and those who test positive are provided immediate ART according to Uganda national HIV treatment and prevention guidelines. Approximately, 50 HIV-positive women are identified per month. IDI Kasangati will work directly with the Kitebi KCCA facility, including antenatal care/PMTCT programs, to identify pregnant HIV-positive women attending PMTCT B+ services. Health care workers and study staff at Kitebi ANC clinic will provide general information sessions to inform potential participants.

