### Care for HIV-positive male partners

This study will identify male partners who are HIV-positive, either as part of testing male partners of unknown status, or during follow-up of initially HIV-negative men. Study staff will provide participants with their HIV test results in the context of post-test counseling. Men identified as HIV-positive will be referred for HIV clinical care, including primary care and antiretroviral therapy, according to Ugandan guidelines. During the course of the study, it is possible that guidelines will change regarding clinical care of persons with HIV (including optimal therapy, prophylaxis, etc.). At all times during the study, treatment and referral practices for HIV-positive persons in the study will adhere to national ART guidelines. After the study ends, HIV-positive participants will be provided referrals to other care programs for ongoing HIV primary care. This type of care will also be offered to initially HIV-negative study participants who become positive during follow-up.

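### POC viral load results are placed under South African guidelines in a Uganda-only trial, so the rule for acting on a result could differ between the Aim 2 arms

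*Protocol*

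**What the plan says.** The Protocol section Management of Viral Load Results opens with the intervention arm: routine monitoring on the standard-of-care schedule, GeneXpert in place of the laboratory assay, and testing next to the clinic. That paragraph closes with "Results will be managed according to SoC South African guidelines".

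The following paragraph turns to the control side: "The clinical decisions from the SOC VL testing will adhere to the Ugandan guidelines". It then prints the only algorithm in the protocol:

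- below 50 copies/mL: continue routine monitoring;
- 50-999 copies/mL: counsel and repeat at six months;
- 1,000 copies/mL or more: counsel and repeat at three months; if the result is again 1,000 or more, "participants will be considered for switching to second line treatment according to Uganda guidelines".

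Two other places bear on women's care without separating the arms. Antenatal and postnatal care states: "HIV-positive pregnant women will access routine care at antenatal clinics according to guidelines for preventing and treating HIV infection in Uganda". Table 5 has a row reading "Referral for / provision of ART according to national guidelines".

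The background section POC HIV Viral Load adds one response specific to the POC arm: "Women who are randomized to POC VL who have VL >200 c/ml will receive additional adherence counseling, following the STREAM protocol".

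**The concern.** Aim 2 asks whether POC testing with same-day adherence counseling improves viral suppression at 6 months post-partum compared with laboratory testing. For the contrast to mean that, what follows a raised result should otherwise be the same in both arms, apart from declared parts of the intervention. Naming one country's guidelines for POC results and another's for laboratory results breaks that on paper.

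There is also a practical problem. The section tells staff when to repeat a test and when to consider second-line therapy in pregnant and breastfeeding women. For POC women it points to a guideline that the protocol does not print at that place, and then prints a Ugandan algorithm whose scope is not stated clearly.

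**Working it through.** No plan figure is at issue, so the check is a comparison of texts followed by a simple count.

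**1. What the South African sentence refers to.** It directly follows the sentence on where GeneXpert testing is done, in a paragraph about the intervention arm. The next sentence, "The clinical decisions from the SOC VL testing will adhere to the Ugandan guidelines", is limited to standard-of-care testing. Read in place, the South African sentence is about POC results.

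**2. The two readings of the printed algorithm.**

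| Reading | Consequence for POC results |
|---|---|
| Algorithm covers standard-of-care testing only | POC results fall under a South African rule that the protocol does not set out |
| Algorithm covers both arms (general section heading, participants not labeled by arm) | The South African sentence conflicts with it directly |

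Neither reading leaves the sentence sound.

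**3. Whether the rest of the protocol supports a South African rule.** The Summary and Overall design place the trial in Kampala only. Routine care ("HIV-positive pregnant women will access routine care at antenatal clinics according to guidelines for preventing and treating HIV infection in Uganda") and ART provision ("Referral for / provision of ART according to national guidelines") carry no arm split, whereas the two viral load rows of the same Table 5 are labeled by arm. These entries concern routine care and ART provision, not action on a viral load result. They fit a Ugandan rule for everyone but do not by themselves contradict the sentence. The conflict lies inside Management of Viral Load Results.

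**4. How many women are covered.** Figure 3 has two POC cells of 50: 50 + 50 = 100 of 200, or 50%. The protocol numbers its arms inconsistently, but the count is the same under each numbering.

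**5. How many results.** POC tests are scheduled at enrollment, delivery and 6 months post-partum. The last is the endpoint, so two scheduled results come before it: 2 × 100 = 200. This is a count of scheduled tests, not a ceiling. Table 5 allows antenatal POC tests as indicated, and the algorithm itself triggers repeats.

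**6. How many women would reach a decision in doubt.** Every decision at issue needs a result of 50 copies/mL or more. The protocol gives no rate for the POC arms before the endpoint. As an illustration only, take the 60-80% standard-of-care suppression that the power section assumes at 6 months post-partum: 100 × (1 − 0.80) = 20 to 100 × (1 − 0.60) = 40 women. Considering a switch needs two results of 1,000 or more, so it would involve fewer women than that.

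**The case against.** The strongest reply is that this is a stray phrase with no proven consequence. Only one algorithm is printed, its heading is general, it speaks of participants without naming an arm, and it ends in a Ugandan switch rule. The section also opens by putting intervention-arm routine monitoring on the standard-of-care schedule. A sensible site would probably apply the Ugandan algorithm to everyone. Much of this stands, and it is why the effect may be zero. It does not clear the sentence: repeats triggered by a raised result are not plainly routine monitoring, and the sentence that places the algorithm under Ugandan guidelines is worded for standard-of-care testing.

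A second reply is that South African management might be intended, since POC counseling follows the South African STREAM study. The protocol adopts that study for one purpose only, "Women who are randomized to POC VL who have VL >200 c/ml will receive additional adherence counseling, following the STREAM protocol". It does not extend it to repeat testing or switching.

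A reader might infer more than the document supports in two ways:

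- **That the Aim 2 comparison is biased.** This would need the two national rules to differ in content. The South African rule is not given, so neither a difference nor its direction can be shown.
- **That several sections flatly contradict the sentence.** Besides the entries on routine care and ART provision, Recruitment ("those who test positive are provided immediate ART according to Uganda national HIV treatment and prevention guidelines") concerns starting ART. The statement that "treatment and referral practices for HIV-positive persons in the study will adhere to national ART guidelines" stands in the section on male partners. Both point toward national rules, but neither addresses action on a woman's viral load result.

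**Conclusion.** The point holds as an error in an operative clinical rule. The governing guideline for acting on a viral load result is named differently for POC and laboratory testing, in a trial run only in Uganda, with no reason given. It covers 100 of 200 women and leaves unclear the timing of repeat tests after a raised result and the rule for considering second-line treatment.

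The effect on the Aim 2 comparison is of unknown size and direction. If the two national rules agree, only the text is wrong; if they differ and the sentence is followed, the arm contrast carries that difference as well. Table 4, the endpoint definition and the analysis do not change. The conclusion rests on reading the South African sentence as referring to POC results, which its position supports. It does not depend on the illustrative 20-40 women.

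**What to change.** In Management of Viral Load Results, replace the South African sentence with a statement that the printed Ugandan algorithm governs repeat testing and second-line switching for both POC and laboratory results in all four arms. In the same place, name the additional counseling above 200 c/ml as an intended component of the POC arms, so that it is not mistaken for a departure from the algorithm.

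Leave the delivery-visit viral load schedule out of this change. Overall design gives Arm 3 a laboratory test at delivery, while Table 5 marks a delivery test only in the POC row. That is a separate inconsistency and should not be settled silently here.

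The cost is one sentence replaced and one or two added, with the matching line in the site procedures. No visits, tests or participants are added.
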